## 8.2 Documenting Adverse Events

AEs spontaneously reported by the subject and/or in response to an open question from the study personnel or revealed by observation will be recorded during the study at the investigational site. For each AE, the Investigator will evaluate and report the onset (date and time), resolution (date and time), severity, causality, action taken, serious outcome (if applicable), and whether or not it caused the subject to discontinue the study. The AE term should be reported in standard medical terminology when possible.

## 8.3 Reporting Adverse Events

All AEs (related and unrelated) will be recorded from the time of the written ICF signature up to the end of the study, whether or not they are related to the IP. Any SAEs considered related to the IP and discovered by the Investigator at any time after the study should be reported.

All SAEs must be reported immediately and no later than 24 hours of awareness by submitting an SAE Report Form as indicated below.

To:	Email: [contact] US-only [contact] (*fax should only be utilized as back-up to email) Ex-US Fax number: +44 (0)[contact] (*fax should only be utilized as back-up to email)
------------	---

Additional follow-up information, if required or available, should all be reported within 1 business day of receipt, should be completed on a follow-up SAE form, placed with the original SAE information, and kept with the appropriate section of the eCRF and/or study file.

The Sponsor or designee will work with the Investigator to ensure that all the necessary information is provided within 1 calendar day of initial receipt for fatal and life-threatening events and within 5 calendar days of initial receipt for all other SAEs.

The Sponsor or designee is responsible for notifying the relevant regulatory authorities of certain events globally. It is the Principal Investigator's responsibility to notify the IRB/IEC of all SAEs that occur at his or her site. Investigators will also be notified of all unexpected, serious, drug-related events (7/15 Day Safety Reports) that occur during the clinical study. Each site is responsible for notifying its IRB/IEC of these additional SAEs. Marketing authorization holder (MAH) or designee is responsible for notifying the relevant regulatory authorities of certain events in Japan.

## 8.4 Other Events Requiring Immediate Reporting

### 8.4.1 Pregnancy and Lactation

Pregnancy in a female study subject who has received IP is required to be reported to the Sponsor or designee immediately and no later than 24 hours of awareness, by email or fax, using the Clinical Trial Drug Exposure During Conception/Pregnancy Report Form (see [Section 8.3](#) for contact information).

Subjects who become pregnant during the study period must not receive additional doses of IP but will not be withdrawn from the study. If the subject requests to know which treatment she

received, this information will be provided to her. The pregnancy will be followed for outcome of the mother and child (including any premature terminations) and the outcome information should be reported to the Sponsor or designee immediately and no later than 24 hours of awareness (see [Section 8.3](#) for contact information).

Should the Investigator become aware of a pregnancy in the partner of a male study subject who has received IP, this should be reported to the Sponsor or designee immediately and no later than 24 hours of awareness, by fax or email, using the Clinical Trial Drug Exposure During Conception/Pregnancy Report Form (see [Section 8.3](#) for contact information). The Sponsor will endeavor to collect follow-up information on such pregnancies provided the partner of the study subject provides consent.

#### Participants With Partners Who Become Pregnant (or Were Pregnant at the Time of Enrollment)

- In the event a participant's partner becomes pregnant during treatment (or is pregnant at the time of enrollment), and for an additional 6 months after the last dose of IP, the information will be recorded on the Pregnancy Notification Form ([Figure 4](#)). The form must be submitted to the Sponsor's Global Patient Safety immediately and no later than 24 hours of the Investigator's awareness of the pregnancy. (Note: Sites are not required to provide any information on the Pregnancy Notification Form that violates the country or region's local privacy laws).
- Participants with pregnant partners or whose partners become pregnant during treatment and for an additional 6 months after the last dose of IP must practice sexual abstinence or use a barrier method of contraception (as described above) through 6 months after the last dose of IP.
- The Investigator will attempt to obtain a signed consent for release of pregnancy and infant health information directly from the pregnant partner to obtain additional pregnancy information.
- After obtaining the pregnant partner's signed consent for release of pregnancy and infant health information, the Investigator will collect pregnancy outcome and infant health information on the pregnant partner and their baby and complete the pregnancy questionnaires. This information will be forwarded to the Sponsor's Global Patient Safety.
- Generally, infant follow-up will be conducted up to 12 months after the birth of the child (if applicable).
- Any termination of the pregnancy will be reported to the Sponsor's Global Patient Safety regardless of fetal status (presence or absence of anomalies) or indication for procedure.

#### Collection of Lactation Information

- Investigator will collect lactation information on any participant who breastfeeds while taking IP through 6 months after the last dose of IP.
- Information will be recorded on the Lactation Notification Form (see below) and submitted to the Sponsor's Global Patient Safety immediately and no later than 24 hours of the Investigator's awareness of the event.

- Study treatment will be discontinued if a participant breastfeeds during the study as described in the exclusion criteria (see [Section 5.2](#)).
- With the participant's signed consent for release of parent and infant health information, the Investigator will collect mother and infant health information and complete the lactation questionnaire on any participant who breastfeeds while taking IP through 6 months after the last dose of IP.

**Figure 4      Pregnancy and Lactation Notification Forms (Paper-based Form)**

AMGEN Form		
TITLE Clinical Trial Drug Exposure During Conception/Pregnancy	DOCUMENT NO FORM-510390	VERSION 1.0
	EFFECTIVE DATE 25 Apr 2024	PAGE Page 1 of 4

For healthcare professional use only

Subject ID/Number:		Protocol Number:		Country:	
Data Concerning Mother and Father / Family History					
Parents		Trial Participant/Patient		Age (years)	
Mother	 Yes, subject number:			 No	
Father	 Yes, subject number:			 No	
Hereditary diseases, malformations, chronic disease of expectant parents and in their families:		 Yes (if yes, please specify):  No  Unknown			
Previous Pregnancies					
Number of previous pregnancies:					
Number of healthy children ( no birth defects):					
Number of children with birth defect: If any with birth defect please list (use 1 line per child):					
Sex (m/f)		Birth Defects			
Number of induced abortions:					
Number of spontaneous abortions:					
Number of stillbirths:					
Current Pregnancy					
Pregnancy is already terminated:  Yes  No*  Unknown					
*Week of gestation at the time of reporting:					
First day of last menstruation:					
Expected due date:					
Period regular:  Yes  No  Unknown					
Drugs Used by the Trial Participant or Patient (Mother or Father)					
Drug/IMP	Daily Dose (unit)	Indication		Therapy Date (from-to) dd-mmm-yyyy	
Drugs Used by the Mother During Pregnancy					

AMGEN®		
Form		
TITLE Clinical Trial Drug Exposure During Conception/Pregnancy	DOCUMENT NO FORM-510390	VERSION 1.0
	EFFECTIVE DATE 25 Apr 2024	PAGE Page 2 of 4

Subject ID/Number:		Protocol Number:		Country:	
Trade Name/INN	Daily Dose (unit)	Mode of Application	Indication	Therapy Date (from-to) dd-mmm-yyyy	
 Please tick if additional page is attached					
Course of Pregnancy					
Prenatal Examinations	Date	Normal	Abnormal	If abnormal, please specify	
Amniocentesis					
Testing of alpha-foetoproteins					
Chorionic villus sampling (CVS)					
Genetic Screening					
Ultrasound (US):					
1 st US (9 th to 12 th week of gest.)					
2 nd US (19 th to 23 rd week of gest.)					
3 rd US (28 th to 32 nd week of gest.)					
Regular preventive medical checkups:		 Yes  No  Unknown			
Potential Risks (drug, smoking, alcohol, x-ray examinations, etc.) and complications (e.g., hospitalization, infections during pregnancy, etc.)		 Yes (if yes, please specify):  No  Unknown			
Data Concerning Childbirth and Child					
Outcome of Pregnancy:					
Date of Birth / Abortion / Stillbirth:      or  Unknown					
Gestation Week	Vaginal Birth	Caesarian	Ventouse/Vacuum Extractor	pH of cord blood	

AMGEN Form		
TITLE Clinical Trial Drug Exposure During Conception/Pregnancy	DOCUMENT NO FORM-510390	VERSION 1.0
	EFFECTIVE DATE 25 Apr 2024	PAGE Page 3 of 4

Subject ID/Number:		Protocol Number:		Country:							
											
Child	Sex	APGAR Score			Circumference of the Head	Birth Weight and Height		Fetal Lie	Outcome*	Abnormality	
	m/f	1	5	10	cm	Kg	Cm			Yes	No
1											
2											
3											
*Outcome: 1. Live-birth 2. Spontaneous abortion (up to 20 th week) 3. Stillbirth (20 th – 27 th week) 4. Stillbirth (from 28 th week) 5. Induced abortion 6. Death of mother and child 7. Ectopic pregnancy, e.g. tubal pregnancy											
Were there any complications during childbirth?						 Yes, please specify:  No  Unknown, please specify:					
Does the child have any birth defect? (Please also specify in cases of induced or spontaneous abortion, stillbirth, or death of neonate)						 Yes, please specify:  No  Unknown, please specify:					
### 5. Breast Feeding Information

Did the mother breastfeed or provide the infant with pumped breast milk while actively taking an Amgen product? ☐ Yes ☐ No

If No, provide stop date: mm \_\_\_\_/dd \_\_\_\_/yyyy \_\_\_\_

Infant date of birth: mm \_\_\_\_/dd \_\_\_\_/yyyy \_\_\_\_

Infant gender: ☐ Female ☐ Male

Is the infant healthy? ☐ Yes ☐ No ☐ Unknown ☐ N/A

If any Adverse Event was experienced by the mother or the infant, provide brief details: \_\_\_\_\_

\_\_\_\_\_  
\_\_\_\_\_

#### **8.4.2 Overdose or Misuse**

Any instance of overdose of IP (suspected or confirmed) must be reported within 24 hours by submitting an SAE Report Form as indicated in [Section 8.3](#). Any associated AEs and SAEs must also be reported, and their management should be recorded.

#### **8.5 Adverse Events of Special Interest**

An AESI is an event of scientific and medical interest specific to the understanding of the IP and which may require close monitoring and collection of additional information by the Investigator. An AESI may be serious or non-serious.

The following events are considered AESIs for this study:

- Anaphylaxis and serious hypersensitivity reactions
- IRRs
- Immune complex disease
- Cytopenia
- Serious and/or opportunistic infections, including PML. See [Appendix 4](#) for a list of opportunistic infections.

Once an AE is identified as an AESI, it should be reported within 24 hours by submitting an SAE Report Form as indicated in [Section 8.3](#).

For anaphylaxis, serious hypersensitivity reactions, and IRRs, additional details will be captured in the eCRF.

#### **8.6 Medical Monitor Coverage**

Each subject will be provided with contact information for the Investigator. In addition, each subject will receive a phone number intended to provide the subject's physician access to a medical monitor 24 hours a day, 7 days a week, in the event of an emergent situation where the subject's health is deemed to be at risk. In this situation, when a subject presents themselves to a medical facility where the treating physician or healthcare provider requires access to a physician who has knowledge of the IP and the clinical study protocol and the Investigator is not available, the treating physician or healthcare provider can contact a medical monitor through this system.

#### **8.7 Regulatory Reporting Requirements for Safety Information**

If participant is permanently withdrawn from IP because of a serious adverse event, this information must be submitted to the Sponsor or designee.

Prompt notification by the Investigator to the Sponsor of serious adverse events is essential so that legal obligations and ethical responsibilities towards the safety of participants and the safety of a study treatment under clinical investigation are met.

The Sponsor has a legal responsibility to notify both the local regulatory authority and other regulatory agencies about the safety of a study treatment under clinical investigation. The Sponsor will comply with country-specific regulatory requirements relating to safety reporting to the external review body and Investigators.

Individual safety reports for suspected unexpected serious adverse reactions will be reported by the Sponsor according to local regulatory requirements (eg, electronic submission to the Eudravigilance database in the EU as per EU Clinical Trial Regulation 536/2014) as well as the Sponsor policy and forwarded to Investigators as necessary.

An Investigator who receives an individual safety report describing a serious adverse event or other specific safety information (eg, summary or listing of serious adverse events) from the Sponsor will file it along with the Investigator's Brochure and will notify the external review body, if appropriate according to local requirements.

To comply with worldwide reporting regulations for serious adverse events, the treatment assignment of participants who develop serious, unexpected, and related AEs may be unblinded by the Sponsor before submission to regulatory authorities. Aggregate analyses may also be unblinded by the Safety Assessment Team, as appropriate. Investigators will receive notification of related serious adverse events reports sent to regulatory authorities in accordance with local requirements.

The Sponsor will prepare a single Development Safety Update Report (DSUR) (also referred to as Annual Safety Report in the EU) for the IP. To ensure that consolidated safety information for the study is provided, this single DSUR will also include appropriate information on any other IP used in the clinical study, if applicable.

## 9 STATISTICAL CONSIDERATIONS

### 9.1 General Considerations

Tabular summaries will be presented by treatment group. Categorical data will be summarized by the number and percentage of subjects in each category. Continuous variables will be summarized by descriptive statistics.

This section summarizes the planned statistical analyses. Further details will be provided in a comprehensive statistical analysis plan (SAP), which will be prepared prior to randomization of the first subject, with final amendments completed prior to database lock. Any deviations from this plan will be reported in the Clinical Study Report.

### 9.2 Determination of Sample Size

The primary endpoint is the change from baseline in MG-ADL score at Week 26 in the overall study population (ie, the AChR-Ab+ and MuSK-Ab+ populations). Sample sizes were estimated using a 2-sided t-test. Approximately 230 subjects (188 subjects with AChR-Ab+ MG and 42 subjects with MuSK-Ab+ MG) will be randomized in a 1:1 ratio to either inebilizumab or placebo. This sample size will provide more than 95% power to detect a true mean (population) treatment difference of 2 in the overall study population with a 2-sided 0.05 alpha level, assuming a common standard deviation of 4 using a 2-sided t-test.

The sample size of AChR-Ab+ subjects was also estimated using a 2-sided t-test, which will provide at least 90% power to detect a true mean (population) treatment difference of 2 in change from baseline of MG-ADL with a 2-sided 0.05 alpha level. The sample size of MuSK-Ab+ subjects was estimated based on the feasibility of the enrollment. Assuming a common standard deviation of 4 and a 2-sided 0.05 alpha level, the minimum detectable difference in the MuSK-Ab+ population is 2.5.

### 9.3 Analysis Sets

**Full Analysis Set:** The “Full Analysis Set” (FAS) will include all subjects randomized who received at least 1 dose of IP in the study and have baseline and at least 1 postbaseline observation. Subjects will be analyzed according to the treatment randomized. The efficacy analysis will be based on the FAS.

**Safety Analysis Set:** The “Safety Analysis Set” will include all subjects who received any dose of IP during the RCP. Subjects will be analyzed according to the treatment that they actually received. The safety and ADA analysis in the RCP will be based on the Safety Analysis Set.

**Open-label Analysis Set:** The “Open-label Analysis Set” will include all subjects who received any dose of inebilizumab during the OLP.

**Any Inebilizumab Analysis Set:** The “Any Inebilizumab Analysis Set” will include all subjects who received any dose of inebilizumab.

**Pharmacokinetic Analysis Set:** The “PK Analysis Set” will include all subjects who received IP and have at least 1 quantifiable serum PK observation post first dose. Subjects will be analyzed according to the treatment that they actually received. The PK analysis will be based on the PK Analysis Set.

**Per-protocol Analysis Set:** The “Per-protocol Analysis Set” (PAS) will include all subjects in the FAS who are sufficiently compliant with the protocol. Major reasons to exclude subjects from the PAS analysis set are listed below:

[REDACTED]

The protocol deviations will be reviewed and documented prior to the database lock. The efficacy analysis based on the PAS will be conducted for primary and key secondary endpoints as a sensitivity analysis.

## 9.4 Methods for Statistical Analyses

[REDACTED]

Treatment-policy strategy: The analyses will include all data captured during the RCP, defined as the period after randomization to the conclusion of the last scheduled RCP visit regardless of the rescue therapy use.

While on-treatment strategy: The analyses will include all data captured during the RCP, defined as the period after randomization to [REDACTED] after the last treatment visit regardless of the rescue therapy use.

All efficacy analyses described below apply to the RCP unless stated otherwise. For subjects in the OLP and/or in the SFU Period, the efficacy may also be summarized over the combined study periods (ie, combined RCP and OLP, etc.) to characterize the durability of the treatment effect, if applicable.

The safety endpoints will be summarized for the RCP, OLP, combined RCP and OLP, and SFU if applicable, respectively.

### 9.4.1 Analysis of the Primary Efficacy Endpoint

The primary endpoint is the change from baseline in MG-ADL score at Week 26 in the overall study population (ie, the AChR-Ab+ and MuSK-Ab+ populations).

For the primary analysis, the primary estimand is defined as follows:

- Population: Subjects in the FAS.
- Variable (endpoint): change from baseline in MG-ADL score at Week 26.
- Intercurrent events:
  - Rescue therapy initiated on or after Day 28 during the RCP will be analyzed using a composite strategy. The data collected on or after the initiation of the rescue therapy will be imputed using the subject's worst observation collected before initiation of the rescue therapy.
  - Rescue therapy initiated before Day 28 during the RCP and treatment discontinuation will be analyzed using a treatment policy strategy. Subjects who discontinue treatment early will be asked to attend scheduled evaluations until the end of the RCP. The data collected after treatment discontinuation for reasons other than death or rescue therapy will be included in the analysis.
- Population-level summary: Mean difference between inebilizumab and placebo.

Rationale for estimand: The occurrence of the intercurrent event of rescue therapy is informative about the effect of treatment. If a subject is administered rescue therapy after Day 28, it may be considered that the allocated treatment was not effective, and the subject was not successfully treated. Taking rescue therapy will confound treatment effect. The intercurrent event of treatment discontinuation is considered to be part of the treatments being compared, reflecting the Intention-to-treat principle.

Supplementary analysis will be performed for the primary efficacy endpoint using a treatment policy strategy to address both intercurrent events of rescue therapy and treatment discontinuation (ie, including data collected after rescue or therapy and treatment discontinuation in the analysis). Details will be specified in the SAP.

The primary endpoint will be analyzed using a mixed-effects model for repeated measures (MMRM) analysis with covariates of treatment group, baseline antibody status (AChR-Ab+ or MuSK-Ab+), visit, the interaction of visit and treatment group, baseline steroid use, baseline QMG score, and baseline MG-ADL score. The estimate of the treatment effect estimator will be based on a contrast from this MMRM model. The variance-covariance matrix will be assumed to be unstructured. If the procedure doesn't converge, then a compound symmetric variance-covariance matrix will be applied.

To assess the robustness of the treatment effect, for each estimand, additional sensitivity analyses utilizing multiple imputation (MI) approaches will also be conducted with the missing data imputed for the subjects who discontinue the study early based on the different missing data mechanism assumptions, including those expected to be more conservative such as missing not at random. For example, the missing data would be imputed

[REDACTED]

[REDACTED]. Full details of the analyses will be prespecified in the SAP.

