#### 9.4.4 Analysis of Exploratory Efficacy Endpoints

#### 9.4.5 Multiplicity Control

The type I error will be controlled at 0.05 (2-sided) across the primary and the key secondary endpoints. A hierarchical approach will be applied for multiplicity control, and the testing strategy is proposed as follows:

- Step 1: Test the primary endpoint at a significance level of 0.05; if the p-value is  $< 0.05$ , then proceed to Step 2. Otherwise, no null hypothesis is rejected.
- Step 2: Test the key secondary endpoints at a significant level of 0.05 sequentially at alpha level 0.05 in the following order:
  - Change from baseline in QMG score at Week 26 in the overall study population.
  - Change from baseline in MG-ADL at Week 26 in the AChR-Ab+ population.
  - Change from baseline in QMG score at Week 26 in the AChR-Ab+ population.
  - Change from baseline in MG-ADL at Week 26 in the MuSK-Ab+ population.
  - Change from baseline in QMG score at Week 26 in the MuSK-Ab+ population.

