### 9.5 Planned Analyses

**Primary analyses:** The primary analysis will be conducted when all subjects have completed Week 26 or, if a subject discontinues early from the study before Week 26. All efficacy and safety data collected during the RCP and prior to the data cut-off for the primary analysis will be analyzed. In addition, the safety data collected during the OLP and prior to the data cut-off will also be analyzed. The AChR-Ab+ subjects who haven't completed the RCP will complete the remaining visits during the RCP per protocol.

**Final analysis:** The final analysis will be conducted when all subjects have completed (or discontinued early from) the study.

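### The primary MMRM's only fallback, compound symmetry, gives too small a Week 26 standard error if it is ever used and variance rises over visits

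*Protocol*

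**What the plan says.** Protocol 9.4.1 analyses the primary endpoint with an MMRM that contains a visit-by-treatment interaction. On covariance it says "The variance-covariance matrix will be assumed to be unstructured", and that, if this fit fails to converge, "then a compound symmetric variance-covariance matrix will be applied". SAP 3.4.2.2 states the same two-step rule. On inference it says "The estimate of the treatment effect estimator will be based on a contrast from this MMRM model"; the endpoint fixes that contrast at Week 26.

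No intermediate structure and no robust standard error appear in the readable text. Part of the SAP's model description is blacked out, but the covariance sentences are legible in both documents and the Protocol's model paragraph can be read in full.

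For the key secondary endpoints, Protocol 9.4.2 gives covariates but no covariance structure, and SAP 3.4.3.2 is redacted straight after naming the MMRM.

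Protocol 9.4.5 states: "The type I error will be controlled at 0.05 (2-sided) across the primary and the key secondary endpoints". Neither document says whether visits after Week 26 enter the Week 26 model.

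**The concern.** The test concerns one visit. Compound symmetry pools all visits into a single variance and all visit pairs into a single correlation, so the Week 26 contrast is judged against the visit-averaged variance. If early visits vary less than Week 26, that average is too low, the confidence interval too narrow and the p-value too small.

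No SD by visit is given, but the design makes a rise plausible. The Week 2 MG-ADL is taken before the second dose. The steroid taper begins at Week 4 and runs to Week 24 on schedules that depend on entry dose (Protocol Table 12). Worst-observation replacement applies only to rescue from Day 28 (Protocol 9.4.1).

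A fallback in a confirmatory plan matters only when it is used, and then it should hold its level. At stake is the nominal 5% of any test in the hierarchy that is run on it.

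**Working it through.** **Inputs from the documents**
- Protocol 9.2: "more than 95% power to detect a true mean (population) treatment difference of 2 in the overall study population", "assuming a common standard deviation of 4 using a 2-sided t-test"; 230 subjects randomised 1:1, of whom 188 are AChR-Ab+ and 42 MuSK-Ab+; two-sided alpha 0.05.
- Protocol Tables 3 and 4: MG-ADL after baseline at Weeks 2, 4, 8, 12, 18 and 26 (six visits, so 6×7/2 = 21 covariance parameters). QMG has no Week 2 assessment (five visits, 5×6/2 = 15 parameters).

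**Assumption:** the Week 26 SD is 4, and the SD rises linearly in weeks from f × 4 at Week 2, with f = 0.9, 0.7 or 0.5.

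**The plan's own figures reproduce.** With 115 per arm the standard error is 4 × √(2/115) = 0.527 and power for a 2-point difference is 96.5%. With 94 per arm power is 92.6%. With 21 per arm the smallest significant difference is 2.021 × 4 × √(2/21) = 2.49, matching the stated 2.5.

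**Formula.** With complete data and a visit-by-treatment term, the Week 26 contrast under compound symmetry is the difference in Week 26 means, but its model variance uses the mean of the visit variances. Hence

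SE ratio = √(mean visit variance / Week 26 variance), and type I error = 2 × [1 − Φ(1.96 × ratio)].

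**MG-ADL, worked for f = 0.7.** The SDs are 2.8, 2.9, 3.1, 3.3, 3.6 and 4.0. The variances are 7.84, 8.41, 9.61, 10.89, 12.96 and 16, with sum 65.71 and mean 10.95. The ratio is √(10.95/16) = 0.827, so the model SE is 0.436 where the true one is 0.527. Type I error is 2 × [1 − Φ(1.622)] = 10.5%.

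| Week 2 SD / Week 26 SD | MG-ADL mean variance | SE ratio | Type I error, MG-ADL | Type I error, QMG |
|---|---|---|---|---|
| 0.9 | 14.17 | 0.94 | 6.5% | 6.3% |
| 0.7 | 10.95 | 0.83 | 10.5% | 9.6% |
| 0.5 | 8.35 | 0.72 | 15.7% | 13.7% |
| 1.0 (constant) | 16 | 1.00 | 5.0% | 5.0% |

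The QMG column uses the same line without Week 2; only the ratio of SDs matters.

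**Shape of the rise.** Reaching 10% requires mean variance / Week 26 variance of 0.704 or less. That is a Week 2 SD of about 2.9 or less under linear growth, 2.5 under square-root growth, and 2.0 if the SD levels off at Week 12.

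**Visits to Week 52 included.** Continue the same line to Weeks 32, 38, 44 and 52, with 188 subjects at each. For f = 0.7 the late SDs are 4.3, 4.6, 4.9 and 5.3, and their variances sum to 91.75. The pooled variance is (230 × 65.71 + 188 × 91.75) / (230 × 6 + 188 × 4) = 15.18, the ratio 0.974 and the type I error 5.6%. For f = 0.9 and 0.5 it is 5.3% and 5.4%. If instead the SD stays flat after Week 26, it is 7.5% to 11.8% for Week 2 SDs from 3.0 down to 1.5.

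**Simulation check.** REML compound symmetry fits with the Protocol's covariates (antibody status omitted at N = 42), 3,000 null trials per setting, with 0% or 12% dropout:
- Week 2 SD 2.0 (f = 0.5): 15.1% to 16.7% at N = 230, and 15.4% to 16.5% at N = 42.
- Constant variance: 4.5% to 5.5% and 4.7% to 5.6%.
- Same fits with an uncorrected sandwich SE, all settings: 4.4% to 6.4% at N = 230, but 6.0% to 7.4% at N = 42.
- Week 26-specific variance (Week 26 ANCOVA), all settings: 4.1% to 6.0% and 4.4% to 6.3%.

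**The case against.** The strongest reply is that the harm needs two events the documents do not show.

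*Failure of the unstructured fit.* In a simulation with six visits, 10% to 20% dropout and 3% sporadic missingness, the unstructured REML fit failed in 0 of 650 trials at n = 42 and 0 of 40 at n = 230. That exercise used normal data, no worst-observation replacement and an optimiser other than SAS, so it does not exclude failure. It does show that 21 parameters on 42 subjects need not fail.

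*Rising variance.* It is plausible but not documented.

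Both points stand, and they rule out several stronger readings a reader might infer:
- **That the plan breaks its 0.05 control.** The percentages above are conditional on the fallback. If it were used 5% of the time, independently of the result, overall error would be 0.95 × 5% + 0.05 × 10.5% = 5.3%, or 5.5% using 15.7%.
- **That the primary model is at risk because ten visits need 55 parameters.** The rule that "All efficacy and safety data collected during the RCP and prior to the data cut-off for the primary analysis will be analyzed" (Protocol 9.5) describes data scope at the cut-off, not which visits enter the model. If late visits did enter and variance kept growing, the inflation nearly vanishes.
- **That the fallback governs the MuSK-Ab+ models.** Readable text states it only for the primary model. Extending it to the key secondary analyses is reasonable but inferred.
- **That no robust standard error is planned.** One could sit in redacted SAP text; the most that can be said is that none is readable.

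What the reply does not remove is that the stated fallback can lose its level in the case it is written for, while better fallbacks are readily available.

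**Conclusion.** The point holds in conditional form. If the unstructured primary model fails and the variance of change from baseline rises over visits, the Week 26 standard error under compound symmetry is too small. For a linear rise from 90%, 70% or 50% of the Week 26 SD, type I error is about 6.5%, 10.5% or 15.7% for MG-ADL. QMG is somewhat less affected, and with constant variance there is no inflation. These figures rest on an assumed variance pattern and on modelling visits to Week 26 only. The probability that the fallback is used is unknown and has not been shown to be high. This is a cheap improvement to a contingency rule, not evidence that the primary analysis as planned is invalid.

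**What to change.** Amend the covariance paragraph in SAP 3.4.2.2, keep Protocol 9.4.1 consistent with it, and say whether it also governs the key secondary models:

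1. Before compound symmetry, prespecify an ordered list of structures that let the variance differ by visit. For example: heterogeneous Toeplitz; then heterogeneous AR(1), or a spatial version that respects the unequal spacing of Weeks 2, 4, 8, 12, 18 and 26; then heterogeneous compound symmetry.
2. For any structure other than unstructured, use an empirical (sandwich) standard error with a small-sample correction. The 6.0% to 7.4% at N = 42 shows that the plain sandwich is not enough in a MuSK-Ab+ analysis.
3. State that the Week 26 models use visits through Week 26 only.

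The cost is one SAP paragraph, and slightly wider intervals if the fallback is used.
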